## **IV. Post test**

Program Component	Intro/ Pre-test	History of vapes	Chemical in vapes, and reaction to inside the body	Mental Health	How to change addictive behaviors	Resources	Questions / Recap	Post-test
Brief Description	Introducing the program to the targeted population and having the students take a 5 minute pre-test.	Students will learn about the history of vapes and tobacco.	Students will learn about nicotine and its addictive properties. Students will learn how these things affect the lungs, heart, and teeth	Students will learn how the brain functions and how it reacts to contents in vapes.	Helping the students identify their triggers and learning behaviors to change their point of view.	Providing the students resources within their community	Going back over the main bullet points from the curriculum and letting the students ask questions	Students will take a 5 minute post-test
Duration (in minutes)	5	3	5	3	5	3	5	5

## 4. STUDY ENROLLMENT AND WITHDRAWAL

### 4.1. Study Inclusion Criteria:

- The program's targeted population is starting at the middle school grade levels, up to college.
- Live in the DFW metroplex
- Willing to participate throughout the presentation

### 4.2. Study Exclusion Criteria:

- Less than 12 years old
- Students that are not in the DFW metroplex

### 4.3. Premature Termination or suspension of study

Unforeseen unless unable to collect data due to lack of subject participation.

## 5. STATISTICAL CONSIDERATIONS

## 5.1. Sample Size Considerations

A power analysis using the G-power 3.1 computer program (Faul & Erdfelder, 2009) indicated that a total sample of 35 people would be needed to detect a medium effect (Cohen's  $dz = 0.5$ ) with 80% power using matched-pairs Wilcoxon signed-rank test with alpha at 0.05 and assuming non-normal distribution. We need to enroll at least 44 subjects to account for 20% attrition rate. We plan to enroll 100 subjects in this study from whom we will collect pre- and post-test data on vaping.

## 5.2. Statistical Analysis Plan

Descriptive analysis will be performed for all continuous variables. Mean  $\pm$  standard deviation will be presented for normally distributed variables and median  $\pm$  interquartile range will be presented for non-normal variables. Count and proportions will be presented for all categorical variables. All normally distributed continuous outcomes will be analyzed with paired t test and non-normally distributed continuous outcomes will be analyzed with nonparametric Wilcoxon signed-rank test. All Categorical outcomes will be analyzed using McNemar test.

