**2. OBJECTIVES AND STUDY OUTCOME MEASURES**

**2.1.** Study Objectives

**2.1.1.** Primary Objective(s)

The primary objective for this program is to obtain an understanding and gather information on the percentage of vape users in teens and young adults. This study will include at least 100 individuals, as this will allow us to determine why vaping is so prominent, what causes individuals to be attracted towards this habit, and determine why there is an increasing rate of vaping.

**2.1.2.** Secondary Objective(s)

The secondary objective for this program is to prevent those who do not vape to not begin to partake in this habit and to reduce the percentage pf the target population who are currently vaping, by increasing their knowledge on the dangers of vaping by 10%.

**2.2.** Study Outcome Measures

**2.2.1.** Primary Outcome(s)

We will obtain the percentage of vape users and their reasons for vaping from information gathered from pre-test (Appendix C). Within 6 months, we hope to see a decline in the usage of vapes in the DFW area.

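### Section 5.2 plans no paired change or confidence interval for the knowledge score, so the 10% gain set in 2.1.2 cannot be read properly from the planned output

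*Combined protocol and SAP*

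**What the plan says.** Section 5.2 chooses both summary and test by whether a variable is normally distributed. Normal outcomes get mean, SD and a paired t test. For the rest, "non-normally distributed continuous outcomes will be analyzed with nonparametric Wilcoxon signed-rank test", and the median with "interquartile range will be presented for non-normal variables". Categorical outcomes go to McNemar. The section does not define the knowledge score, say how or on which variable normality is judged, or name a pre-post difference or a confidence interval.

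Section 5.1 sizes the study on the non-normal branch: "80% power using matched-pairs Wilcoxon signed-rank test with alpha at 0.05", "assuming non-normal distribution".

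The target is in the secondary objective (2.1.2): "increasing their knowledge on the dangers of vaping by 10" percent, without saying whether relative or in percentage points. Knowledge change is a secondary outcome (2.2.2). The primary outcome (2.2.1) is the percentage of vape users and their reasons. Section 1.2 counts ten post-test questions and aims for at least eight correct. Two of the ten in Appendix C (feeling pressured, likelihood of use) have no correct answer, which leaves eight that can be scored.

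**The concern.** A 10% gain is a statement about magnitude. A p-value shows only that scores shifted, and two medians of a coarse score are a poor gauge of how far. The non-normal branch could print equal medians before and after with p < 0.05 when the target was met. It could also print a full one-point rise when the true gain was about half a point. A reader could not tell from either result whether 2.1.2 was achieved. The normal branch would at least let a reader subtract two means, but no interval is planned there either.

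**Working it through.** **1. The plan's own figure.** Inputs from 5.1: dz = 0.5, alpha 0.05 (two-sided assumed), power 80%. The usual method for the signed-rank test is a noncentral t with effective size N × ARE. With ARE = 3/π (normal parent) and N = 35:

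- effective N = 35 × 0.955 = 33.4
- noncentrality = 0.5 × √33.4 = 2.89
- power = 0.801

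Attrition: 35 / 0.80 = 43.75, so 44. Both stated figures, 35 and 44, reproduce. The cautious minimum-ARE option gives 39, or 39 / 0.80 = 48.75, so 49, still below the planned 100. The sizing is sound for a test; it does not address precision of an estimate.

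**2. What each branch of 5.2 delivers for the 10% target.**

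| Branch | Summary | Test | Paired change | CI |
|---|---|---|---|---|
| Normal | pre and post mean, SD | paired t | not planned (means can be subtracted) | not planned |
| Non-normal | pre and post median, IQR | Wilcoxon | not planned | not planned |

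**3. Size of a 10% gain.** With K scored items and baseline proportion correct p (p is not in the documents; 50-70% assumed here):

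- relative reading: K × p × 0.10. For K = 8: 8 × 0.5 × 0.10 = 0.40 to 8 × 0.7 × 0.10 = 0.56 points
- percentage-point reading: K × 0.10 = 0.8 points (K = 8) or 1.0 point (K = 10)

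**4. What a median can show.** With n even, the median of a whole-number score moves in steps of 0.5, and takes a half value only when the two middle ordered scores differ. From a baseline median of 4, the possible rises are 0, 0.5/4 = 12.5%, 1/4 = 25%, and so on.

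**5. How often the two medians are equal although knowledge truly rose by 10%.** Simulated with n = 100 (a few runs with 80). Assumptions, none from the documents: baseline 40-70% correct; abilities vary between students (beta with concentration 15, or logit SD 0.5-1.0); the post-test either keeps items already correct and adds new ones, or is redrawn independently. Ranges span these choices.

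| Reading of 10% | 8 items | 10 items |
|---|---|---|
| Relative | roughly 35-70% | about 6-69% |
| Percentage points | 3-24% | 1-12% |

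For 8 items, a relative gain and baseline 50-70%, the median rose by 1 point or more in about 21-50% of studies. On the percentage-point reading it showed a full point in 69-94%, for a true gain of 0.8.

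**6. Which branch is likely.** 5.2 names no normality check. If Shapiro-Wilk were used on the paired differences, it would reject in 76-100% of runs at n = 100 and 17-100% at n = 35. On the raw 8-item scores (n = 80-100) it rejected in every run.

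**7. Test against estimate.** Wilcoxon power was within about 2 percentage points of the paired t test at n = 100 and within about 5 at n = 35.

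**8. The mean paired change (8 items, relative gain, n = 100).** It recovered the true gain, with a standard error of about 0.06-0.19. Half-width = 1.984 × SE, or about 0.1-0.4 points, before any clustering by classroom session.

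**The case against.** Several points on the other side are fair.

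- A reader might infer that the normality rule is why the gain goes unestimated. It is not the sole cause: the normal branch plans no paired difference or interval either.
- A reader might infer that medians generally fail to move. That depends on the relative reading of 10% and on a short score. The protocol states neither the reading nor an eight-item score, and on the percentage-point reading equal medians are uncommon.
- A reader might infer that the study's main result is at risk. The documents rank knowledge change as secondary, and they also carry goals that are naturally proportions (eight of ten correct in 1.2; at least half more aware in 1.4), for which 5.2 plans counts and proportions.
- A reader might infer that Wilcoxon is the wrong test, or that the score must be declared non-normal. Step 7 is against the first. On the second, the rule is conditional and the check unstated.
- The median and IQR might be meant for the change itself. This is possible, but it does not rescue the relative reading: with 10 items and n = 100 the median paired change was exactly zero in 20-100% of runs.
- The confidence interval may not decide the target. For an estimated gain of 0.40 and a half-width of 0.38, the interval is 0.40 ± 0.38 = 0.02 to 0.78 points, close to zero at one end and nearly twice the target at the other.

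These limit the claim but do not remove it. The proportion goals are different targets, and a wide interval still shows how much the data say about the gain, which two medians and a p-value do not.

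**Conclusion.** The point holds in limited form. Section 5.2 specifies no within-student change and no confidence interval for the knowledge score in either branch, although 2.1.2 sets a numerical gain. In the branch that 5.1 assumes, pre and post medians are a poor guide to that gain. They hide a true relative 10% rise in roughly 35-70% of studies if eight items are scored. On the percentage-point reading they seldom hide it, but with eight items they usually show 1 point for 0.8. These frequencies rest on the assumed baseline, student variation and learning models. The missing estimate and interval do not depend on those models.

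The documents do not support going further. The outcome is secondary, the Wilcoxon test is adequate, and 35, 44 and 100 are unaffected. This should be corrected because it is cheap and a stated target cannot otherwise be properly judged.

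**What to change.** In 5.2, for the knowledge score and whatever the normality result:

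- Define the score on the items common to both tests that have a correct answer (pre-test 5-11 and 13; post-test 1-7 and 9), with an answer key.
- State whether 10% is relative to the baseline mean or in percentage points.
- Report the mean within-student change, post minus pre, with a 95% CI, also as a percent of the baseline mean, and read the target against the estimate and its interval.
- Keep Wilcoxon as the supporting test, and show the full pre and post score distributions.

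The cost is a few lines of text, but the scored items and the meaning of 10% must be settled first. No new data items are needed: the change requires each student's two papers to be linked, as the paired tests in 5.2 already do. The report should say plainly that the interval may be too wide to decide firmly on a relative 10% target, more so if scores cluster by classroom session.

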### 2.2.2. Secondary Outcome(s)

Changes in the degree of understanding will be assessed from the results of the pre- and post-test (Appendix C). In addition, we hope to find the answers to the following questions:

- Is vaping within the student's environment?
- Are the students being socially peer pressured into smoking, and if so how often?
- Are most students forming addictive behaviors towards vaping?
- What are the triggers that cause a student to vape?
- What is their reasoning on why they vape or participate in any smoking products?
- Do members of their close group of friends' vape?
- Are students aware of the serious and long-term side effects of vaping?

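### Section 5.2 names no main pre/post test and no multiplicity rule: if nothing truly changes, the chance of at least one false positive is about 10-14% with two or three tests and about 20-43% with eleven

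*Combined protocol and SAP*

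**What the plan says.** - **Section 5.2** gives paired t or Wilcoxon signed-rank tests for continuous outcomes, depending on normality. For the rest it says: "All Categorical outcomes will be analyzed using McNemar test". It states no significance level, main comparison, order or adjustment.
- **Section 5.1** holds the only significance level. It reports that "a total sample of 35 people would be needed to detect a medium effect". The calculation is for one signed-rank test at the 0.05 level, with power of 80% and a dz of 0.5, and normality is not assumed. The outcome for this test is not named. A score is the natural reading, because dz and a signed-rank test suit a score and not a yes/no item. The section adds: "We need to enroll at least 44 subjects to account for 20% attrition rate". Planned enrolment is 100.
- **Section 2.2.1** names a primary outcome: the percentage of vape users and their reasons, taken from the pre-test. Change in understanding between the two forms is secondary (2.2.2), with no item or score singled out.
- **Section 1.2** sets a goal of 8 correct answers out of 10 on the post-test (objective 3) and fewer students likely to vape in future (objective 4).
- **Appendix C**: post-test items 1-10 repeat pre-test items 5-14, so ten items are paired. Pre-test items 1-4, on current and past use, are not repeated.

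**The concern.** Section 5.1 spends its 0.05 and its 80% power on one comparison, but 5.2 does not reserve that 0.05 for any comparison. Nothing elsewhere fills the gap. Success is described in several ways: 8 of 10 correct and fewer likely to vape (1.2), at least 50% of participants more aware (1.4), a 5% fall in users (1.4.1) and a 10% gain in knowledge (2.1.2). None is tied to a test in 5.2.

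Once the data are in, whichever comparison falls below 0.05 could be matched to one of these aims and reported as evidence that the program works. Sections 1.2 and 3 give publishing data in support of vaping education as the study's purpose, so a reader needs to know which result was meant to carry the claim.

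**Working it through.** **1. The plan's own figure.** For a signed-rank test with a normal parent distribution, the effective sample size is N × 3/π. With N = 35 this is 35 × 0.955 = 33.4, the noncentrality is 0.5 × √33.4 = 2.89, and two-sided power at 0.05 is 0.801. So 35 is reproduced. One-sided testing would need 28, so 5.1 appears to be two-sided, although it does not say so. For attrition, 35 / 0.80 = 43.75, rounded up to 44. With 100 enrolled, 100 × 0.80 = 80 pairs remain. The calculation covers one test only.

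**2. How many tests 5.2 implies.** Section 5.2 speaks of outcomes, not items, so the count depends on the reading.

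- Narrow: the score and likelihood of vaping (two tests), or these plus the 8-of-10 goal (three).
- Wide: ten shared items plus the score (eleven). Three shared items are true/false and five more can be reduced to right/wrong. The other two, pressure to vape (three options) and likelihood of use (four options), need a collapsing rule before a standard McNemar test, and 5.2 gives none.

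**3. Independent tests, no true change, each at 0.05.** P(at least one p < 0.05) = 1 − 0.95^k.

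| k | Set | Result |
|---|---|---|
| 1 | one designated test | 5.0% |
| 2 | score, likelihood | 9.8% |
| 3 | plus the 8-of-10 goal | 14.3% |
| 8 | right/wrong items only | 33.7% |
| 10 | all shared items | 40.1% |
| 11 | all shared items plus score | 43.1% |

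**4. Allowing for dependence.** The score is built from the items, and the items may move together. The eleven-test set was simulated with no true change. The assumptions, none of which come from the documents, were 60% correct on each item, latent pre/post correlation 0.5 and 3,000 runs per setting. The score was the number correct on eight items, tested by signed-rank. The correlation below is between items in their latent pre-to-post change. Paired figures are for 80 and 100 pairs.

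| Correlation | Asymptotic McNemar | Exact McNemar |
|---|---|---|
| 0 | 42.8%, 41.7% | 29.0%, 28.9% |
| 0.3 | 41.7%, 38.8% | 26.4%, 27.0% |
| 0.6 | 37.9%, 37.2% | 24.1%, 26.2% |
| 0.9 | 33.2%, 31.7% | 20.4%, 20.9% |

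The simulation standard error is at most about √(0.4 × 0.6 / 3,000) = 0.9 percentage points. A second simulation had 80 pairs, item base rates of 0.12 to 0.85, a shared factor of 0.3, a retest correlation of 0.6 and a paired t test on the score. It gave 41% (asymptotic) and 26% (exact), inside the same range.

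The two- and three-test values were not simulated. The 8-of-10 goal is a cut of the score, so 14.3% is on the high side for that set.

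**The case against.** The strongest reply is that the plan never says each item is an outcome. Read with 1.2 and 2.2.2, it has two or three paired outcomes, and the excess over 5% is modest. This stands as a reading. A reader might infer that 5.2 as written produces eleven tests and a false-positive chance of about 40%. The documents do not fix the count, and 40% is near the top of the range even when all eleven are run.

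It also stands that the no-change case is a reference condition. The post-test closes the same session of about 35 minutes that teaches several of the answers, so some knowledge items will probably improve. If the eight knowledge items truly changed and only pressure and likelihood did not, the chance of a false claim on those two would be 1 − 0.95² = 9.8%, assuming independence.

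Three other stronger readings fail:

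- That 5.2 sets 0.05 for each test. The level is carried over from 5.1.
- That the study has no primary outcome. Section 2.2.1 names one; what is missing is a main pre/post test.
- That the pressure item cannot change and only adds noise. The content described in 1.1 includes ways of handling peer pressure, and 2.2.2 lists peer pressure among its questions, so this is an open question that the study set itself.

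Finally, this is a single-group classroom study with a descriptive primary outcome, and sections 7.5 and 9 plan no item-level claims. That limits the harm but does not remove the gap: 5.2 assigns hypothesis tests to all outcomes, and nothing says which one decides.

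**Conclusion.** The concern holds in this form: no pre/post comparison is designated as the main one, and no order or adjustment is given, although the study is sized for a single test at 0.05. If nothing truly changes and 0.05 is used each time, the chance of at least one false positive is about 10-14% for two or three outcomes and about 20-43% for ten items plus the score. The first range assumes independence. The second spans the simulated settings and the independence value, and depends on item correlation and on exact or asymptotic McNemar. Every value is above 5%, and the spread comes mainly from the plan not saying what will be tested. Sample size is no obstacle to a remedy: about 80 pairs are expected against 35 required.

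**What to change.** In section 5.2:

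1. Name the change in knowledge score as the single main pre/post test at 0.05. Define the score as the number correct on the eight shared items that have a right answer (post-test items 1-7 and 9), with a fixed answer key. State in 5.1 that this is the outcome the sample size refers to.
2. Test likelihood of future vaping (objective 4) at 0.05 only if the first test is significant, with its four categories collapsed by a rule fixed in advance. This order keeps the familywise error for the two claims at 5%.
3. Report all other items, including the pressure item, as before/after percentages with confidence intervals, labelled descriptive.
4. State that the primary outcome in 2.2.1 stays descriptive. Say also that the main test does not address the 5% fall in users in 1.4.1, since the use questions are not repeated on the post-test.
5. Reconcile the 8-of-10 goal in 1.2 with the scorable items. Only eight can be marked, so as written the goal amounts to a perfect score.

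Cost: single items can no longer be claimed as significant. The change needs an amendment with IRB review (6.2). Section 10 lists $345 for an amendment without revised consent, or $345 × 1.30 = $448.50 with indirect cost. No extra participants or data are needed.

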## **6. ETHICS/PROTECTION OF HUMAN SUBJECTS**

### 6.1. Ethical Standard

The investigators will ensure that this study is conducted in full conformity with the principles set forth in The Belmont Report: Ethical Principles and Guidelines for the Protection of Human Subjects of Research, as drafted by the US National Commission for the Protection of Human Subjects of Biomedical and

Behavioral Research (April 18, 1979) and codified in 45 CFR Part 46 and/or the International Conference on Harmonization (ICH) E6. The investigators will conduct all aspects of this study in accordance with all national, state, and local laws or regulations.

The investigators will ensure that all individuals involved in research involving human subjects will adhere to the following principles: minimize the risk of harm, obtain informed consent, protect anonymity and confidentiality, avoid deceptive practices, and provide the subject the right to withdraw participation. This will be an anonymous study, and all participant names will not be included.

## **6.2. Institutional Review Board**

The protocol and all study-related materials will be submitted to the IRB for review and approval. Protocol approval will be obtained before any participant information and clinical data are collected. Only approved documents will be used for patients. Any amendment to the protocol will require review and approval by the IRB before study changes are implemented.

## **6.3. Informed Consent / HIPAA Waiver**

### **Informed Consent**

Study subjects will not be provided an informed consent form due to the study being anonymous and confidential within an educational setting. There are no risk associated with this study and no names or identification will be presented on participants documents. Participants will be asked to state their zip code and grade level on the pre and post-test in order to gather our data. Consent to participate is obtained without coercion or undue influence.

## HIPAA Waiver

Requesting the IRB for a waiver of consent for the following reasons:

- This research is not regulated by the FDA.
- This research involved no more than minimal risk to the subjects.
- The waiver or alteration will not adversely affect the right or welfare of the subjects.
- The research could not practicably be carried out without the waiver
- It is not feasible to provide subjects with pertinent information after participation.
- No patient interaction will occur.
- No patient interventions will occur.

### 6.4. Participant Confidentiality

Participant confidentiality will be strictly maintained at all times with all information used being non-traceable to the participants. This study will be anonymous as participants names will not be on any documents or test.

Information will only be accessed by the principal investigator or sub-investigators. No identifiable participant data will be disclosed. All information obtained will be source de-identified, presented on a large scale, and not traceable to any one particular individual. All data collected will be kept on the password protected hospital server, and only authorized trained personnel will have access to the share drive. All physical information will be shredded in the lock shred box located in the Cancer Administration Program office. At close of this study, all identifiers will be removed from the data collection tools.

